6.4 Secondary Efficacy Analysis

Incidence of adverse events up to 8 weeks after the last dose of Pembrolizumab will be measured.

6.5 Safety Analysis

The safety data which include adverse events (AEs) and serious adverse events (SAEs) will be tabulated for the two cohorts. AEs and SAEs will be summarised by description, frequency, outcome, severity, seriousness and relationship to study treatment. Additionally, SAEs will also be summarised by SAE reason. Serious Adverse Reaction (SAR), Suspected Unexpected Serious Adverse Reaction (SUSAR) and other safety variables (e.g. pregnancy and lactation) and their frequencies, if any, will also be reported.

6.6 Secondary Analysis

The analysis of efficacy variables, clinical and laboratory measurements will be done using all the measurement points or visit dates.

Compliance with the study medication will be assessed based on patient diaries. Compliance will be measured by the percentage of treatment delays noted in each patient. The median and range of the compliance measure will be reported.

Data on concomitant medications will be summarized by: drug name, reason for therapy, therapy dosage / units, frequency of therapy and route of administration.

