## 5.8 Study Schedules during Treatment

Table 3 summarizes the trial procedures to be performed at each visit. Individual trial procedures are described in detail below. Treatment is divided into cycles of 21 days, with visits and assessments specified according to the relevant cycle.

Unless otherwise indicated, scheduled assessments may take place within  $\pm 3$  days of the specified visit. Assessment days are relative to the start of study treatment i.e. Cycle 1 Day 1.

If a patient has a treatment break, please contact the Clinical Trials Section (CTS) for advice regarding the timing of research blood assessments. All other assessments, including laboratory safety assessments, vital signs and radiological imaging should continue to be performed.

CUPem	C/37/2017	Imperial College London	V7.0; 08.12.2021
-------	-----------	----------------------------	------------------

Furthermore, additional evaluations/testing may be deemed necessary by the Sponsor and/or MSD for reasons related to subject safety. In some cases, such evaluation/testing may be potentially sensitive in nature (e.g., HIV, Hepatitis C, etc.), and thus local regulations may require that additional informed consent be obtained from the subject. In these cases, such evaluations/testing will be performed in accordance with those regulations.

**During the COVID-19 pandemic, patients whom are under ongoing treatment can be offered longer intervals of 1 to 2 weeks between treatment to avoid peak COVID-19 capacity issues.**

CUPem	C/37/2017	Imperial College London	V7.0; 08.12.2021
-------	-----------	----------------------------	------------------

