### 6.5 Compliance

The importance of treatment compliance should be emphasised to the patient. Each patient will be given a patient diary to note the date of their treatment and the dose of study treatment administered.

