3.6 Schedule of Time and Events

Table 3 summarizes the trial procedures to be performed at each visit. Individual trial procedures are described in detail below. Treatment is divided into cycles of 21 days, with visits and assessments specified according to the relevant cycle.

Unless otherwise indicated, scheduled assessments may take place within ± 3 days of the specified visit. Assessment days are relative to the start of study treatment i.e. Cycle 1 Day 1.

If a patient has a treatment break, please contact the Clinical Trials Section (CTS) for advice regarding the timing of research blood assessments. All other assessments, including laboratory safety assessments, vital signs and radiological imaging should continue to be performed.

Furthermore, additional evaluations/testing may be deemed necessary by the Sponsor and/or MSD for reasons related to subject safety. In some cases, such evaluation/testing may be potentially sensitive in nature (e.g., HIV, Hepatitis C, etc.), and thus local regulations may require that additional informed consent be obtained from the subject. In these cases, such evaluations/testing will be performed in accordance with those regulations.

During the COVID-19 pandemic, patients whom are under ongoing treatment can be offered longer intervals of 1 to 2 weeks between treatment to avoid peak COVID-19 capacity issues.

Table 2: Schedule of Assessments

Trial Period:	Screening Phase	Treatment Cycles								End of Treatment	Post-Treatment		
Treatment Cycle/Title:	Study Screening	1	2	3	4	5	6	7	8	Discon	Safety Follow-up	Follow Up Visits	Survival Follow-Up
Scheduling Window (Days):	-28 to -1		± 3	± 3	± 3	± 3	± 3	± 3	± 3	At time of Discon	30 days post discon	Every 8 weeks post discon	Every 12 weeks
Administrative Procedures													
Pre-screening Visit													
Informed Consent	X												
Inclusion/Exclusion Criteria	X												
Demographics and Medical History	X												
Prior and Concomitant Medication Review	X	X	X	X	X	X	X	X	X	X	X		
Trial Treatment Administration		X	X	X	X	X	X	X	X				
Trial Treatment Compliance		X	X	X	X	X	X	X	X				
Quality of Life Questionnaire (EORTC QLQ-C30)	X					X				X			
Post-study anticancer therapy status											X	X	X
Survival Status		X	X	X	X	X	X	X	X	X	X	X	X
Clinical Procedures/Assessments													
Review Adverse Events	X	X	X	X	X	X	X	X	X	X	X		
Full Physical Examination	X ^a	X			X				X	X	X		
Directed Physical Examination	X ^a	X	X	X	X	X	X	X	X	X	X	X	

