5.9 Disease Details and Treatments

Prior Cancer Treatments - include systemic treatments, radiation and surgeries.

Post Study Anti-Cancer Therapy Status - all new anti-neoplastic therapy initiated after the last dose of trial treatment. If a subject initiates a new anti-cancer therapy within 30 days after the last dose of trial treatment, the 30 day Safety Follow-up visit must occur before the first dose of the new therapy. Once new anti-cancer therapy has been initiated the subject will move into survival follow-up.

Treatment Compliance - is detailed record of the date and time of administration and drug dose all study treatment that are captured in the patient diary. The number of missed or delayed doses will be reported for each patient and compliance will be reported as the percentage of treatment delays.

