Abnormal – not clinically significant					n (%)							
Abnormal – clinically significant					n (%)							
BMI												
Raw value					Median [IQR]							
Obese					n (%)							
Normal					n (%)							
Undernourished					n (%)							
ECOG												
0					n (%)							
1					n (%)							
2					n (%)							
3					n (%)							
4					n (%)							
5					n (%)							
Pregnancy					n (%)							
Lactation					n (%)							

Table 16. Treatment Compliance summary

	Cohort 1	Cohort 2
Number of patients with delayed treatments		
Percentage of patients with delayed treatments		
Mean number of delayed treatments among patients		
Mean percentage of delayed treatments among patients		

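### Compliance is measured only as the percentage of delayed treatments, so missed infusions do not enter it, permitted delays count against the patient, and no SAP table shows how much drug was delivered

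*SAP*

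**What the plan says.** SAP 6.6 names the data source: "Compliance with the study medication will be assessed based on patient diaries". It then gives the measure: "Compliance will be measured by the percentage of treatment delays noted in each patient". The result is to be summarised as a median and range.

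SAP 5.9 says: "The number of missed or delayed doses will be reported for each patient and compliance will be reported as the percentage of treatment delays". That sentence treats missing a dose and delaying a dose as different things and promises a count, but the compliance measure it defines uses delays alone.

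SAP 6.11, Table 16, has four rows: the number and the percentage of patients with delayed treatments, the mean number of delayed treatments, and "Mean percentage of delayed treatments among patients". There is no row for missed doses. None of SAP Tables 1 to 16 shows infusions received, cumulative dose or dose intensity.

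The protocol allows or requires several kinds of delay. Section 5.8 (repeated in SAP 3.6) says that patients on treatment during the pandemic "can be offered longer intervals of 1 to 2 weeks between treatment". Section 3.3.1 with Table 2 requires treatment to be withheld for listed toxicities. The text after Table 2 permits interruptions for medical, surgical or logistical reasons. Section 3.4 sets a dosing window of 3 days either side of Day 1.

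On records, protocol 6.5 says: "Each patient will be given a patient diary to note the date of their treatment and the dose of study treatment administered". Protocol 10.4 separately requires the site to enter administration of the study drug in the EDC system.

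**The concern.** The measure describes timing, but it is labelled and reported as compliance. A missed infusion reduces the drug a patient receives and leaves the score unchanged. A late infusion that follows the protocol worsens the score. Neither section of the SAP exempts permitted or required delays, defines a delay, links it to the 3-day window, or states a denominator.

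The trial has one arm and one regimen, 200 mg every 3 weeks. A reader of its results needs to know how closely patients received that regimen, and Table 16 as drafted does not say. The source is also second best: the drug is infused in clinic and the site holds the administration record, yet the patient diary is the stated basis.

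**Working it through.** The documents give no compliance figure to reproduce. The check applies the SAP's measure literally to constructed patients. The patient profiles are illustrations, not forecasts.

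**Formulas**
- SAP measure = delayed treatments / treatments × 100. The denominator is not stated, so both doses given and doses planned were tried.
- Proportion of doses given = doses given / doses planned.
- Relative dose intensity = (mg given / weeks on treatment) / (200 mg / 3 weeks).

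**Missed doses, none delayed**
- 6 due, 3 missed, 3 given on schedule: 0/3 = 0% or 0/6 = 0% delays. Doses given = 3/6 = 50%. Over 18 weeks, (600/18) / (200/3) = 33.3/66.7 = 50% intensity.
- 8 planned, 3 missed, 5 on schedule: 0/5 = 0% or 0/8 = 0% delays. Doses given = 5/8 = 62.5%.

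**Permitted delays, none missed** (the COVID allowance read as 3 + 1 = 4 or 3 + 2 = 5 weeks)
- 8 planned, 8 given, 4 after an extended interval: 4/8 = 50.0% delays, 100% of doses given.
- 8 planned, 8 given, all 7 after the first extended: 7/8 = 87.5% delays, 100% of doses given.
- Intensity if every interval is 5 weeks: 3/5 = 60%. At 4 weeks: 3/4 = 75%. These credit each dose with its full extended interval. If the last of 8 doses is credited with only 3 weeks, the 5-week case is 24/(7 × 5 + 3) = 24/38 = 63%.

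**Sensitivity to the undefined term**
- One toxicity hold, with the next infusion 12 weeks after the last, in a patient with 8 planned doses. Logged as one delay with all 8 doses still given: 1/8 = 12.5%. Logged as 3 passed infusions missed: 0%.
- If a missed dose were counted as a delay, the patient with 3 of 8 missed would score 3/8 = 37.5% instead of 0%.

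The patient with 50% of planned drug therefore scores better (0%) than the patient with all 8 doses, 7 of them late with permission (87.5%). The choice of denominator does not alter this.

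**Summary statistic.** SAP 6.6 promises median and range. Table 16 gives means for the two per-patient quantities. These need to agree.

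**The case against.** The strongest reply is that little depends on this measure. The default population is intention-to-treat, and the per-protocol set in SAP 4.3 is defined by at least 2 cycles and assessability for toxicity. Response, disease control, PFS, OS and quality of life do not use compliance. That stands: this is a descriptive output.

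A reader might infer that the percentage of delays is the only account of drug delivery. SAP 5.9 does not support that, because it also promises a per-patient number of missed or delayed doses. What remains is that this number is worded as one combined count, is not part of the measure and has no table row.

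A reader might also infer that patients will be labelled compliant or non-compliant. They will not: no cut-off is set, and each patient simply gets a percentage.

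The reversed ordering is not forced by the text. The dosing rules describe holding and restarting, so a passed-over infusion could be logged as a late next one. The 0% score needs missed doses to be kept apart from delayed doses. SAP 5.9's separate terms make that the natural reading, but the absence of a definition leaves it open, and that is itself a gap.

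The 5-week case throughout is an extreme. SAP 3.6 says patients "can be offered longer intervals of 1 to 2 weeks between treatment to avoid peak COVID-19 capacity issues", which points to relief at peaks, and no expected frequency is given.

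Finally, it is tempting to say that under-delivery would explain a weak PFS or OS result. The documents do not show this. Protocol 1.2.2 cites exposure margins of 0.5 to 5.0 in melanoma and target engagement lasting beyond 21 days, and intensities of 50% to 75% are not below 0.5. That does not establish equal efficacy in this disease, but it leaves the effect on efficacy unproven either way.

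**Conclusion.** The point holds as a reporting defect of moderate weight. SAP 5.9, SAP 6.6 and Table 16 measure compliance by delays only. Missed infusions do not enter the measure, and delays that the protocol allows or requires are not exempted. On the literal reading the score can be 0% with 50% of planned drug delivered, and 87.5% with every one of 8 doses delivered.

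This rests on two assumptions: that missed and delayed doses are recorded as distinct events, as SAP 5.9 implies, and that a delay means any dose later than the 3-week schedule. The profiles are illustrative, and the documents give no basis for how often such patients will occur. The consequence is a compliance result that can misstate how much drug was delivered. Analysis populations and efficacy estimates are unaffected.

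**What to change.** In SAP 5.9, SAP 6.6 and Table 16, replace the percentage of treatment delays with the following, taken from site-entered eCRF administration data with the diary as back-up:

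- number of infusions received per patient;
- relative dose intensity, defined as mg given per week on treatment divided by 200 mg per 3 weeks, with a stated rule for when time on treatment ends;
- number of missed doses, separate from delays, with a rule for classifying an infusion passed over during a hold;
- delays beyond the 3-day window, with a stated denominator.

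Use median and range in Table 16 to match SAP 6.6. Where the reason is recorded, split delays into Table 2 hold, COVID extension, other permitted interruption and other.

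The cost is SAP wording and one table shell. Administration dates and doses are already collected, so the first four items need no new data. The split by reason may need some abstraction from source records: the protocol asks for the reason only in the patient's study record, and states this for medical, surgical and logistical interruptions. No treatment rule changes.

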6.7 Data Management

Data management will be performed by CCTS using the InForm electronic data capture (EDC) and management system. The system allows for real time oversight of trial activity including adverse event reporting, rapid data validation and data aggregation.

6.8 Missing Data

No imputation for missing data will be undertaken. The number of missing observations for each variable will be reported.

6.9 Withdrawal from the Study

Withdrawal can occur at any time according to the following reasons: patient decision; lost to follow-up; death, pregnancy or administrative reasons. Patients who withdraw from the study before having at least 2 cycles of Pembrolizumab or before having follow-up tumour or QoL assessment will be excluded from the Quality of Life analysis and some secondary analyses.

6.10 Deviations from the SAP

Any deviation(s) from the final statistical plan in the final analysis will be described and the justification be given in the final report.

6.11 Tables to present

Table 1. Patient Baseline Characteristics *

	Cohort 1 n = 20	Cohort 2 n = 57
Age (yr)		
Sex		
Male		
Female		
Weight (kg)		
Height (m)		
BMI (kg/m²)		
Ethnicity		
White		
Mixed		
Asian		
Black		
Other		
Cell Type of Tumour		
Adenocarcinoma		
Squamous cell carcinoma		
Neuroendocrine		
Poorly differentiated carcinoma		
Poorly differentiated neoplasm		
Histopathological types of CUP		
Well or moderately differentiated adenocarcinomas		
Undifferentiated or poorly differentiated adenocarcinomas or carcinomas		
Squamous cell carcinomas		
Undifferentiated neoplasms		
CUP Subtypes		
Poorly differentiated carcinoma, predominantly nodal disease		
Poorly differentiated neuroendocrine carcinomas		
Peritoneal adenocarcinomatosis of a serous papillary histological type in females		
Isolated axillary nodal metastases in females		
Squamous carcinoma involving non- supraclavicular cervical lymph nodes		
Metastases in bone adenocarcinoma and elevated serum PSA in males		
Poor-risk visceral CUP		

* Data are presented as frequency (percentage) for categorical variables and median [IQR] for continuous variables

Table 2. Concomitant medical conditions at baseline*

Medical condition	Cohort 1 n =	Cohort 2 n =
Medical condition 1		
Medical condition 2		
Medical condition 3		
Medical condition 4		
Medical condition 5		
Medical condition 6		
Medical condition 7		
Medical condition 8		

** Data are presented as number of patients having the medical condition.
A patient may have more than one concomitant medical condition.*

Table 3. Concomitant medications at baseline*

Drug Name and Dose	Cohort 1 n =	Cohort 2 n =
Medication 1		
Medication 2		
Medication 3		
Medication 4		
Medication 5		
Medication 6		
Medication 7		

** Data are presented as number of patients taking the medication. A patient may have more than one concomitant medication.*

Table 4. Summary of Tumour Assessment based on RECIST (irRECIST)

	Baseline	Cycle 5	Cycle 8	Discon	Post Discon
Sum of the diameters for all target lesions (mm)[†]	## (##-##) [n=##]	## (##-##) [n=##]	## (##-##) [n=##]	## (##-##) [n=##]	## (##-##) [n=##]
Proportion of Tumour size change^{†‡}		## (##-##) [n=##]	## (##-##) [n=##]	## (##-##) [n=##]	## (##-##) [n=##]
Overall response (n=)					
Complete response		0 (0%)	0 (0%)	0 (0%)	0 (0%)
Partial response					
Stable disease					
Progressive disease					
Progression before scan					
Withdrawn before scan					
Missing					

[†] Data are presented as median (IQR)

[‡]Proportion change in the sum of the diameters for all target lesions at that follow-up time (or progression if prior to that follow-up time) compared to baseline

Table 5. EORTC QLQ-C30 scores

A. Cohort 1

Scales	Baseline		Month 3		Discon		p-value
	Mean Median	StDev Range	Mean Median	StDev Range	Mean Median	StDev Range	
GHS							
Physical functioning							
Role functioning							
Emotional functioning							
Cognitive functioning							
Social functioning							
Fatigue							
Nausea and vomiting							
Pain							
Dyspnea							
Insomnia							
Appetite loss							
Constipation							
Diarrhea							
Financial difficulties							

B. Cohort 2

Scales	Baseline		Month 3		Discon		p-value
	Mean Median	StDev Range	Mean Median	StDev Range	Mean Median	StDev Range	
GHS							
Physical functioning							
Role functioning							
Emotional functioning							
Cognitive functioning							
Social functioning							
Fatigue							
Nausea and vomiting							
Pain							
Dyspnea							
Insomnia							
Appetite loss							
Constipation							
Diarrhea							
Financial difficulties							

Table 6. Summary of Adverse Events (AEs)*

	Cohort 1		Cohort 2	
	No. of Events	No. of Subjects [†]	No. of Events	No. of Subjects [†]
Total Number of AEs	##	##	##	##
Severity				
Grade 1	## (##.##%)	##	## (##.##%)	##
Grade 2				
Grade 3				
Grade 4				
Grade 5				
Missing				
Relation to study medication				
Definitely				
Probably				
Possibly				
Unlikely				
Not related				
Not assessable				
Missing				
AE expectedness				
Expected				
Unexpected				
Missing				
AE classification				
Not serious				
Serious				

* Data are presented as frequency (percentage) for categorical variables

[†] A patient may have more than one AEs.

Table 7. Severity of AEs*

A. Cohort 1

	Grade					Total
	1	2	3	4	5	
MedDRA 1						
MedDRA 2						
MedDRA 3						
MedDRA 4						
MedDRA 5						
Total†						

B. Cohort 2

	Grade					Total
	1	2	3	4	5	
MedDRA 1						
MedDRA 2						
MedDRA 3						
MedDRA 4						
MedDRA 5						
Total†						

*Data are presented as number of AEs (number of patients having AEs); A patient may have more than one AE in any category and a patient is only shown once in each category, but may have AEs in more than one category.

†Each patient is counted only once in the total for the number of patients

Table 8. Relationship of AEs with study medication*

A. Cohort 1

	Relationship with study medication	
	Possible/ Probable/ Definite	Unassessable/ Unrelated/ Unlikely
MedDRA 1		
MedDRA 2		
MedDRA 3		
MedDRA 4		
MedDRA 5		
Total†		

B. Cohort 2

	Relationship with study medication	
	Possible/ Probable/ Definite	Unassessable/ Unrelated/ Unlikely
MedDRA 1		
MedDRA 2		
MedDRA 3		
MedDRA 4		
MedDRA 5		
Total†		

*Data are presented as number of AEs (number of patients having AEs); A patient may have more than one AE in any category and a patient is only shown once in each category, but may have AEs in more than one category.

†Each patient is counted only once in the total for the number of patients.

Table 9. Summary of Severe Adverse Events (SAEs)*

	Cohort 1		Cohort 2	
	No. of Events	No. of Subjects [†]	No. of Events	No. of Subjects [†]
Total Number of SAEs	##	##	##	##
Reasons for SAE				
Resulted in death	## (##.##%)	##	## (##.##%)	##
Inpatient hospitalisation/ prolongation of existing				
Severity				
Mild				
Moderate				
Severe				
Life threatening				
Death				
Causal relationship to study drug				
Definitely				
Probably				
Possibly				
Unlikely				
Not related				
Outcome				
Resolved				
Persisting				
Fatal				

* Data are presented as frequency (percentage) for categorical variables

[†] A patient may have more than one SAEs.

Table 10. Severity of SAEs*

A. Cohort 1

	Severity					Total
	Results in death	Life threatening	Requires hospitalisation or prolongation of hospitalisation	Results in persistent or significant disability	Medically significant	
MedDRA 1						
MedDRA 2						
MedDRA 3						
MedDRA 4						
MedDRA 5						
Total†						

B. Cohort 2

	Severity					Total
	Results in death	Life threatening	Requires hospitalisation or prolongation of hospitalisation	Results in persistent or significant disability	Medically significant	
MedDRA 1						
MedDRA 2						
MedDRA 3						
MedDRA 4						
MedDRA 5						
Total†						

*Data are presented as number of SAEs (number of patients having SAEs); A patient may have more than one SAE in any category and a patient is only shown once in each category, but may have SAEs in more than one category.

†Each patient is counted only once in the total for the number of patients

Table 11. Relationship of SAEs with study medication*

A. Cohort 1

	Relationship with study medication	
	Possible/ Probable/ Definite	Unassessable/ Unrelated/ Unlikely
MedDRA 1		
MedDRA 2		
MedDRA 3		
MedDRA 4		
MedDRA 5		
Total†		

B. Cohort 2

	Relationship with study medication	
	Possible/ Probable/ Definite	Unassessable/ Unrelated/ Unlikely
MedDRA 1		
MedDRA 2		
MedDRA 3		
MedDRA 4		
MedDRA 5		
Total†		

*Data are presented as number of SAEs (number of patients having SAEs); A patient may have more than one SAE in any category and a patient is only shown once in each category, but may have SAEs in more than one category.

†Each patient is counted only once in the total for the number of patients.

Table 12. Haematology Data*

	Baseline n=	Visit 1 n=	Visit 2 n=	Visit 3 n=	Visit 4 n=	Visit 5 n=	Visit 6 n=	Visit 7 n=
Haemoglobin (g/dl)								
Haematocrit (g/dl)								
RBC ($10^{12}/L$)								
Platelets ($10^9/l$)								
WBC ($10^9/l$)								
Neutrophils ($10^9/l$)								
Lymphocytes ($10^9/l$)								
Monocytes ($10^9/l$)								
Eosinophils ($10^9/l$)								
Basophils ($10^9/l$)								
Coagulation (PT/INR)								
Coagulation (aPTT)								

*Values are presented as median (IQR).

Table 13. Biochemistry Data*

	Baseline n=	Visit 1 n=	Visit 2 n=	Visit 3 n=	Visit 4 n=	Visit 5 n=	Visit 6 n=	Visit 7 n=
Sodium (mmol/L)								
Chloride (mmol/L)								
Bicarbonate (mmol/L)								
Uric acid (μmol/L)								
Blood urea (mmol/L)								
Alanine aminotransferase (ALT) (U/L)								
Aspartate amino- transferase (AST) (U/L)								
Alkaline phosphatase (ALP) (U/L)								
Total bilirubin (μmol/L)								
Direct bilirubin (μmol/L)								
Lactate dehydrogenase (LDH)								
Total protein								
Calcium (mmol/L)								
Potassium (mmol/L)								
Magnesium (mmol/L)								
Glucose (mmol/L)								
Phosphate (mmol/L)								
Albumin (g/L)								

Baseline n=	Visit 1 n=	Visit 2 n=	Visit 3 n=	Visit 4 n=	Visit 5 n=	Visit 6 n=	Visit 7 n=
Free triiodothyronine 3 (FT3) (pmol/L)							
Free triiodothyronine 4 (FT4) (pmol/L)							
Thyroid Stimulating Hormone (TSH) (mIU/L)							

*Values are presented as median (IQR).

Table 14. Urinalysis Data

	Baseline n=	Visit 1 n=	Visit 2 n=	Visit 3 n=	Visit 4 n=	Visit 5 n=	Visit 6 n=	Visit 7 n=
Glucose	0 + ++ +++ >+++							
Total Protein	0 + ++ +++ >+++							
Blood	0 + ++ +++ >+++							
White Blood Cells	0 + ++ +++ >+++							
Dipstick	Normal Abnormal - not clinically significant Abnormal - clinically significant							

Table 15. Other Safety Assessments

	Baseline n=	Visit 1 n=	Visit 2 n=	Visit 3 n=	Visit 4 n=	Visit 5 n=	Visit 6 n=	Visit 7 n=	Visit 8 n=	Visit 9 n=	Visit 10 n=	Visit 11 n=
Vital Signs												
Pulse					Median [IQR]							
SBP					Median [IQR]							
DBP					Median [IQR]							
Temperature					Median [IQR]							
Respiratory rate					Median [IQR]							
ECG												
Normal					n (%)							
Abnormal – not clinically significant					n (%)							
Abnormal – clinically significant					n (%)							
BMI												
Raw value					Median [IQR]							
Obese					n (%)							
Normal					n (%)							
Undernourished					n (%)							
ECOG												
0					n (%)							
1					n (%)							
2					n (%)							
3					n (%)							
4					n (%)							
5					n (%)							
Pregnancy					n (%)							
Lactation					n (%)							

Table 16. Treatment Compliance summary

	Cohort 1	Cohort 2
Number of patients with delayed treatments		
Percentage of patients with delayed treatments		
Mean number of delayed treatments among patients		
Mean percentage of delayed treatments among patients		

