#### 3.3.1 Dose Modification (Escalation/Titration/Other)

Adverse events (both non-serious and serious) associated with pembrolizumab exposure may represent an immunologic aetiology. These adverse events may occur shortly after the first dose or several months after the last dose of treatment. Pembrolizumab must be withheld for drug-related toxicities and severe or life-threatening AEs as per Table 2 below. Also see Section 6.9 for supportive care guidelines.

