### 7.2.2 Causality of Adverse Events

The Investigator will assess causal relationship between the study treatment and each AE.

Unrelated:	No evidence of any causal relationship
Unlikely:	There is little evidence to suggest there is a causal relationship (e.g. event did not occur within a reasonable time after administration of the trial medication). There is another reasonable explanation for the event (e.g. the patient's clinical condition, other concomitant treatment).
Possible:	There is some evidence to suggest a causal relationship (e.g. because the event occurs within a reasonable time after administration of the trial medication). However, the influence of other factors may have contributed to the event (e.g. the patient's clinical condition, other concomitant treatments).
Probable:	There is evidence to suggest a causal relationship and the influence of other factors is unlikely.
Definite:	There is clear evidence to suggest a causal relationship and other possible contributing factors can be ruled out.

CUPem	C/37/2017	Imperial College London	V7.0, 08.12.2021
-------	-----------	----------------------------	------------------

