5.3 Safety variables

Adverse Event (AE) - is any untoward medical occurrence in a patient or clinical trial subject administered a medicinal product and which does not necessarily have a causal relationship with this treatment. An AE can therefore be any unfavourable and unintended sign (including an abnormal laboratory finding), symptom, or disease temporally associated with the use of the trial medication, whether or not considered related to the IMP. Any worsening (i.e., any clinically significant adverse change in frequency and/or intensity) of a pre-existing condition that is temporally associated with the study treatment, is also an adverse event.

Details to be collected in the eCRF for each AE will include:

- AE description
- Date of onset and date of resolution
- Severity
- Seriousness
- Relationship to study treatment
- MedDRA codes and terms according to system organ class, high level term, low level term and preferred term

Severity and Seriousness of Adverse Events

Severity is a measure of intensity whereas seriousness is defined by the criteria in section 7.4 of the protocol. Severity will be assessed using the grading scales found in the National Cancer Institute CTCAE version 4.03 (June 2010) for all adverse events with an assigned CTCAE term. For those events without assigned CTCAE grades, the recommendation on page 1 of the CTCAE that converts mild, moderate and severe into CTCAE grades should be used. A copy of the CTCAE version 4.03 can be downloaded from the Cancer Therapy Evaluation Program website (<http://ctep.cancer.gov>). Any adverse event which changes CTCAE grade over the course of a given episode will have each change of grade recorded on the adverse event eCRF. All adverse events regardless of CTCAE grade will also be evaluated for seriousness.

Causality of Adverse Events

The causal relationship between the study treatment and each AE will be assessed as follows:

Unrelated: No evidence of any causal relationship

- Unlikely: There is little evidence to suggest there is a causal relationship (e.g. event did not occur within a reasonable time after administration of the trial medication). There is another reasonable explanation for the event (e.g. the patient's clinical condition, other concomitant treatment).

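### SAP Tables 8 and 11 put unassessable causality in the not-related column and have no place for missing causality, so by-term related counts are unlabelled lower bounds

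*SAP*

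**What the plan says.** SAP 6.5 lists relationship to study treatment among the attributes by which adverse events (AEs) and serious adverse events (SAEs) are summarised. It gives no rule for an event whose causality is unassessable or was not recorded. The only specification is therefore the set of table shells in SAP 6.11:

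- Table 8 (AEs by MedDRA term) and Table 11 (SAEs by MedDRA term) each have two causality columns, "Possible/ Probable/ Definite" and "Unassessable/ Unrelated/ Unlikely". Neither has a column for missing causality. Entries are numbers of events with numbers of patients; no percentages are shown.
- Table 6 (all AEs) has seven causality rows: five for the levels of the scale, one for "Not assessable" and one for missing.
- Table 9 (all SAEs) has a block headed "Causal relationship to study drug" with the five levels only.

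On how causality is assessed, protocol 7.2.2 states: "The Investigator will assess causal relationship between the study treatment and each AE". It defines five levels: unrelated, unlikely, possible, probable and definite. SAP 5.3 ("The causal relationship between the study treatment and each AE will be assessed as follows") gives the same five. Protocol Appendix D records a yes or a no. None of the three offers or defines an unassessable option. SAP 6.8 rules out imputation and promises a count of missing observations for each variable.

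**The concern.** An event whose cause could not be assessed is not evidence against a drug effect. In protocol Appendix D, a no on causality needs a ground: no exposure, implausible timing, or another cause that is more likely. The *unlikely* level in protocol 7.2.2 rests on little evidence of a causal link or another reasonable explanation. An unassessable event meets none of these tests, yet Tables 8 and 11 place it beside events that do. Table 6 shows that the SAP's authors expected such records and saw them as a separate category, so the shells are not consistent with each other.

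At stake is how harm is reported by term. Protocol 3.3.1 says: "Adverse events (both non-serious and serious) associated with pembrolizumab exposure may represent an immunologic aetiology". That sentence does not concern tabulation, but it explains why a reader would look up individual MedDRA terms. For a rare term, one event in the wrong column decides whether the related count is 0 or 1.

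**Working it through.** The plan states no figure on this point, so there is none to reproduce. The check sets the shells side by side and then bounds the effect.

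**Step 1. Where each kind of record goes.**

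| Place in SAP 6.11 | Five defined levels | Not assessable | Missing |
|---|---|---|---|
| Table 6, all AEs | one row each | own row | own row |
| Table 8, AEs by term | two groups | with unrelated and unlikely | no cell |
| Table 9, all SAEs | one row each | no row | no row |
| Table 11, SAEs by term | two groups | with unrelated and unlikely | no cell |

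For AEs overall, Table 6 shows the unassessed events. It does not cross causality with seriousness or with MedDRA term, so it cannot show which of them were serious or what they were. For SAEs, the pooled column of Table 11 is the only causality cell an unassessable event can occupy.

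**Step 2. Bounds for one term.** Let r be the events rated possible, probable or definite, n those rated unlikely or unrelated, u the unassessable and m the missing, so that N = r + n + u + m.

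- Related column shown: r.
- Other column shown: n + u.
- Not shown in either column: m.
- True related count, taking the recorded ratings as correct: between r and r + u + m.
- Possible understatement of the related share: from 0 to (u + m)/N.

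Examples, all on assumed inputs because the documents give no counts:

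- If u + m is 0% to 10% of events, the related share is understated by 0 to 10 percentage points.
- If r = 0, u = 1 and m = 0, the table shows 0 related events where the supportable statement is 0 to 1.
- If a reader forms a patient-level rate at the planned 31 to 67 patients, one patient is worth 1/31 = 3.2 to 1/67 = 1.5 percentage points. Tables 8 and 11 do not themselves print rates.

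**Step 3. What other tables allow the reader to recover.** If the totals in Tables 7 and 10 cover every event, then N − (r + n + u) = m, so missing events can be recovered by term. In Table 9, the SAE total minus the five causality rows gives u + m for SAEs overall. Subtracting the missing SAEs then leaves u overall. By term, u cannot be recovered, because it is already summed with n. Patient counts cannot be recovered by subtraction at all, since the footnotes allow one patient to appear in more than one category.

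**Step 4. Whether u can be above zero.** The defined scales have no unassessable level. If the eCRF offers only the five levels and all are completed, then u = m = 0 and the shells do no harm. The documents do not show the eCRF options. They do show an unassessable category in Tables 6, 8 and 11.

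**The case against.** The strongest case on the other side is that the column may be empty. The investigator rates each AE on five levels. Protocol 7.4.2 has the chief investigator review every SAE for causality, and protocol 10.3 raises queries for missing data. The *possible* level is also generous: it asks only that "There is some evidence to suggest a causal relationship" and allows the patient's condition to have contributed. A hepatic event with plausible timing in a patient with liver metastases can be rated possible and so counted as related. Protocol 7.1.1 also keeps events unequivocally due to progression out of AE reporting. All of this stands: it limits how often the problem can arise. It does not explain why the shells carry a category that the plan never defines.

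A second argument is that the events stay visible: Table 6 has both rows, SAP 6.8 gives missing counts, and Tables 7 and 10 list every event by term whatever its cause. For AEs overall this is right. It does not cover causality by term or SAEs. The separate reporting of serious adverse reactions in SAP 6.5 does not close the gap either, because SAP 5.3 defines such a reaction as an SAE considered related, which an unassessable event has not been.

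Two stronger readings are tempting, and the documents support neither:

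- A reader might infer that drug-related toxicity is understated whenever causality cannot be assessed. That is so only if the event was in fact drug-related; otherwise the count shown is correct.
- A reader might infer a bias towards the hypothesis that pembrolizumab is better tolerated than chemotherapy. The secondary endpoint in SAP 5.2 is AE incidence, overall and in performance status 2 patients, regardless of cause. Tables 8 and 11 are descriptive, feed no test and have no comparator.

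**Conclusion.** The point holds as a reporting defect. Tables 8 and 11 classify unassessable events with those rated unrelated or unlikely and give missing causality no cell, in conflict with Table 6. If such events occur, the related counts by term are lower bounds that are not labelled as such. The exposure is greatest for SAEs, because Table 9 does not offset Table 11 as Table 6 partly offsets Table 8.

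The size is unknown. It lies between 0 and (u + m)/N for each term, and is zero if only the five defined levels are used and completed, or if no unassessed event was drug-related. The bound assumes that the recorded ratings are correct. The primary analysis, sample size, power and AE-incidence endpoint are unaffected. The change is worth making because it is nearly free and stops unassessed events from being reported by term as not drug-related.

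**What to change.** 1. In Tables 8 and 11, show *Not assessable* and *Missing* in their own columns. Add a footnote giving the related count with and without them. For patients, derive the larger count from the data as patients with at least one event in any of those columns; adding columns would count some patients twice.
2. Add *Not assessable* and *Missing* rows to the causality block of Table 9, to match Table 6.
3. Define *unassessable* in SAP 5.3 and use one term for it throughout, or delete it from all shells if the eCRF does not offer it.

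Moving these events into the related column is a possible convention, but it replaces an unlabelled lower bound with an unlabelled upper bound, and nothing in the documents calls for it. Separate columns presume nothing about cause.

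The cost is a few headings, one derivation and slightly wider tables. The upper count of drug-related events may look less favourable.
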